7.2 Effectiveness Evaluation Methods

7.2.1 Primary Efficacy Endpoints

After treatment, whether the response rate of patients using the Vibrabot vibrating capsules alone reaches 50%.

The definition of the responder is a patient with an average weekly increase of ≥ 1 complete spontaneous bowel movement (CSBM) compared to the baseline.

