3.2 Content of the Clinical Trial

This study is a multi-center clinical trial. Patients are considered eligible for this study if they meet the inclusion criteria and do not meet any of the exclusion criteria. This study plans to include 300 patients with chronic functional constipation to treat with Vibrabot capsules for at least 6 weeks, and ≥ 300 patients with constipation receiving

other treatments concurrently. The patients, based on their treatment needs and preferences, and after comprehensive consideration by clinical doctors, will undergo vibrating capsule treatment, other treatments, or combination therapy. After entering the study, patients should maintain stable dietary intake (including high-fiber diet, fiber supplements, probiotics, etc.) and exercise according to the recommendations of the constipation diagnosis and treatment guidelines.

During the entire clinical study period, patient-related information will be collected according to the specified time points in the protocol to evaluate the response of functional constipation patients with different severity levels to Vibrabot capsules.

Patients are considered eligible for this study if they meet the inclusion criteria and do not meet any of the exclusion criteria. This study plans to include 300 patients with chronic functional constipation to treat with Vibrabot capsules for at least 6 weeks or more.

The patients, based on their treatment needs and preferences, and after comprehensive consideration by clinical doctors, will undergo vibrating capsule treatment. After entering the study, patients should maintain stable dietary intake (including high-fiber diet, fiber supplements, probiotics, etc.) and exercise according to the recommendations of the constipation diagnosis and treatment guidelines.

4. Background of the Clinical Trial

Constipation is characterized by a decrease in bowel movements, dry and hard stools, and difficulty in defecation. With changes in diet, faster pace of life, and social psychological factors, the prevalence of chronic constipation is on the rise. The global incidence of chronic constipation is 14%, while the prevalence of chronic constipation in adults in China is 4.0% to 10.0%. The prevalence of functional constipation in China is 6%. The high-risk groups for constipation include the elderly, women,

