7.1 Trial Procedure

7.1.1 Trial Flow Chart

| | Visit 1 (0~1 day) | Visit 2 (Week 2 ±3 days) | Visit 3 (Week 4 ±3 days) | Visit 4 (Week 6±3 days) | Visit 5 (Week 10 ±3 days) |
|--|-------------------|--------------------------|--------------------------|-------------------------|---------------------------|
| Informed Consent | X | | | | |
| Baseline Information | X | | | | |
| Inclusion/Exclusion Criteria | X | | | | |
| Prescription Vibrabot capsule treatment/Medication treatment | X | X | X | | |
| Guide patients to use the "Vibrabot Health" Official Account | X | | | | |
| Fill out the Baseline Period Questionnaire (including scale) in the Official Account | X | | | | |
| Fill out the Daily Bowel Movement Questionnaire and Constipation Symptom Self-Assessment Scale and Assessment Scale for Quality of Life with Constipation | | X | X | X | X |
| Concomitant treatment | X | X | X | X | X |
| Adverse event | X | X | X | X | X |

正常诊疗流程筛选入组
Screening for Inclusion Based on Normal Diagnosis and Treatment Procedure

| | | | | | |
|--|---|---|---------------------------------------|---|-------|
| 功能性便秘分型(结肠传输时间、肛门直肠测压等) Functional Constipation Subtyping (Colon Transit Time, Anorectal Manometry, etc.) | 通过症状或问诊对便秘分型初步评估 Preliminary Assessment of Constipation Subtype Based on Symptoms or Interview | 可选 Optional | | | |
| 通过评估, 选择其他治疗方法 Selecting Alternative Treatment Methods through Assessment | 使用蔚通胶囊治疗 Treatment with Vibrabot Capsule | | | | |
| 患者填写问卷, 收集数据 Patients Complete Questionnaires to Collect Data | 沪惠保优惠或其他渠道购买 Purchase through Shanghai-Huibo Health Benefits or Other Channels | | | | |
| 不同使用频次 Different Frequency of Use | 不同疗程 Different Treatment Duration | 与其他方法联合治疗 Combination Treatment with Other Methods | 不同严重程度 Various Severity Levels | 对比其他方法治愈 Comparing Treatment Efficacy with Other Methods | |
| 各中心医生端数据共享 Data Sharing among Medical Centers | 定期学术会议讨论 Regular Academic Meetings for Discussion | | | | |
| 蔚通治疗方法不断优化, 形成专家共识 Continuous Optimization of the Vibrabot Treatment Method, Leading to Expert Consensus | 完成总结报告、科技论文, 研究生培养 Completion of Summary Report, Scientific Paper, and Training of Graduate Students | | | | |

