7.2 Secondary Efficacy Endpoints

- 1) Proportion of constipated patients who use/do not use other constipation treatment methods during treatment and after the vibrating capsule treatment and at the end of follow-up;
- 2) Proportion of patients with an average increase of ≥ 1 CSBMs per week compared to the baseline period;
- 3) Proportion of respondents with an average of ≥ 3 SBMs per week during the treatment period;
- 4) Proportion of subjects with ≥ 3 SBMs per week and an increase of ≥ 1 CSBMs during at least 4 weeks of treatment compared to baseline;
- 5) Proportion of patients with an average increase of ≥ 1 CSBMs per week during the follow-up phase compared to the baseline period;
- 6) Proportion of patients with an average of ≥ 3 SBMs per week during the follow-up phase;
- 7) Proportion of patients with a reduction of ≥ 1 point in total PAC-QOL and PAC-SYM scores after treatment compared to the baseline period;
- 8) Proportion of patients with a reduction of ≥ 1 point in total PAC-QOL and PAC-SYM scores after follow-up compared to the baseline period;
- 9) Time of first use of laxative or enema after a course of vibrating capsule treatment (6 weeks);
- 10) Proportion of constipated patients (including different constipation types, occupations, age groups, BMI, gender, and baseline treatment status) responding to vibrating capsule treatment and at the end of follow-up.

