8.1 Statistical Analysis of the Population

Sample Size Calculation

H0: The effectiveness rate of vibrating capsule treatment for constipation $\leq 50\%$

H1: The effectiveness rate of vibrating capsule treatment for constipation $> 50\%$

In a single-group design, if the study goal is to evaluate the effectiveness of vibrating capsule

treatment for constipation and compare it with the expected 50% effectiveness rate, then a one-sample proportion test can be considered for sample size calculation.

Sample size calculation formula for single sample proportion test is:

$$n = \frac{\left[Z_{1-\alpha} \sqrt{P_0(1-P_0)} + Z_{\beta} \sqrt{P_T(1-P_T)} \right]^2}{(P_T - P_0)^2}$$

Where:

- (1) p is the overall expected success rate (here it is estimated that the effectiveness of treating constipation with vibrating capsules is 50%);
- (2) p_0 is the success rate under the null hypothesis (assuming a 40% success rate under the null hypothesis);
- (3) The probability of Type I error α is set to 0.05, and the probability of Type II error β is set to 0.2 (i.e., the statistical power is $1-\beta=0.8$);

At least 191 participants are needed for this study. Assuming a 20% loss to follow-up, the final sample size required is 239. Considering this is a real-world study and taking into account the outpatient volume of the participating center, it is planned to enroll 300 patients who will take vibrating capsules for 6 weeks, and at the same time, include ≥ 300 patients undergoing constipation treatment during the same period.

(1) Full Analysis Set (FAS) is the set of patients that is as close as possible to the ideal implied by the Intention-to-Treat principle. Specifically, in this trial, the FAS is the data set of all patients with baseline evaluation who take at least one capsule treatment/other treatment option. Missing data for primary efficacy endpoints in the FAS will be imputed according to certain rules while missing data for secondary efficacy endpoints will not be imputed.

(2) Per Protocol Set (PPS) is a subset of the FAS and refers to the set of subjects who meet the inclusion criteria, do not meet the exclusion criteria, complete the treatment, and have no protocol violations. Specifically, in this trial, the PPS includes the patients in the FAS who:

- a) complete the full treatment,
- b) meet the inclusion criteria and do not meet the exclusion criteria,
- c) have good compliance with capsule administration/other treatment, and

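### The primary response rate covers patients using capsules alone, but no fixed denominator is defined; if patients who add treatment are excluded and respond less often, the rate is biased upwards

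*Combined protocol and SAP*

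**What the plan says.** Section 7.2.1, repeated in the Protocol Summary, sets one primary endpoint: "whether the response rate of patients using the Vibrabot vibrating capsules alone reaches 50" per cent. A responder has a mean weekly gain of at least one complete spontaneous bowel movement over baseline. No section defines alone.

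These parts of the plan bear on its meaning:

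- Section 3.2 lets patient and doctor choose, so that patients "will undergo vibrating capsule treatment, other treatments, or combination therapy". Combination therapy is thus a route of treatment from the start.
- The first item under Secondary Efficacy Endpoints in Section 7.2 is the "Proportion of constipated patients who use/do not use other constipation treatment methods during treatment", and also after treatment and at the end of follow-up.
- The flow chart in 7.1.1 has the row "Concomitant treatment | X | X | X | X | X", that is, a record at all five visits.
- Section 8.1 says that "the FAS is the data set of all patients with baseline evaluation who take at least one capsule treatment/other treatment option", and describes this set as being as near as possible to intention-to-treat. The per-protocol set, with its conditions on completion and compliance, is secondary.
- The hypothesis ("H0: The effectiveness rate of vibrating capsule treatment for constipation" at most 50%) and the enrolment target ("it is planned to enroll 300 patients who will take vibrating capsules for 6 weeks") are written for capsule treatment, without the word alone.
- The Note in Section 7 does not count a bowel movement as spontaneous if medication was used in the preceding 24 hours.

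**The concern.** The primary result is a single-group proportion held against a fixed 50%. There is no control group in that comparison to absorb a selective denominator, so whoever is left out moves the result directly.

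The endpoint speaks of patients using capsules alone, not of patients prescribed them alone. Secondary endpoint 1 classifies patients by use of other treatment during the course. Followed literally, membership of the primary denominator therefore depends on something that happens after treatment starts and may itself be a consequence of poor response. A patient who adds a laxative in week 3 because the capsule is not working could be removed rather than counted as a non-responder.

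Two analysts working from the same text and the same data could report different primary rates, and the choice could be made after the data are seen.

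**Working it through.** **The plan's own figure.** Section 8.1 gives 191 patients, and then: "Assuming a 20% loss to follow-up, the final sample size required is 239". With its one-sample formula, null 0.40, expected 0.50, two-sided 0.05 and 80% power:

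n = [1.960 × √(0.40 × 0.60) + 0.842 × √(0.50 × 0.50)]² / (0.10)² = 190.7, so 191; 191 / 0.80 = 238.75, so 239.

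Both figures reproduce. They do not settle this point, which is about who is in the denominator. (The calculation uses a 40% null although the written hypothesis uses 50%. That is a separate matter. Everything below is judged against the 50% in the endpoint and in H0.)

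**Inputs for the illustration.** From the plan: 300 capsule patients and the 50% threshold. Assumed, because the documents give no figure: all 300 are capsule-only at Visit 1 with no missing data; the true response rate in them is 45%; a share q adds treatment and is excluded; a fraction r of those excluded are responders.

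**Formula.** Rate read = (0.45 − q × r) / (1 − q), on 300 × (1 − q) patients.

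- q = 0.20, r = 0.20: (0.45 − 0.04) / 0.80 = 0.5125
- q = 0.20, r = 0.30: (0.45 − 0.06) / 0.80 = 0.4875
- q = 0.10, r = 0.20: (0.45 − 0.02) / 0.90 = 0.478
- q = 0.10, r = 0.30: (0.45 − 0.03) / 0.90 = 0.467

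The chance that the observed rate is at least 50% is the exact binomial tail P(X ≥ n/2). The chance of rejecting H0 (at most 50%) uses an upper tail of 0.025, with critical counts of 168/300, 152/270 and 136/240.

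| Leave (q) | Leavers who respond (r) | n kept | Rate read | P(observed ≥ 50%) | P(reject H0) |
|---|---|---|---|---|---|
| none | – | 300 | 45% | 4.6% | <0.1% |
| 10% | 20% | 270 | 47.8% | 25% | 0.3% |
| 10% | 30% | 270 | 46.7% | 15% | 0.1% |
| 20% | 20% | 240 | 51.25% | 67% | 5.3% |
| 20% | 30% | 240 | 48.75% | 37% | 0.8% |

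**Direction.** If r = 0.45, the same as the whole group, the formula returns 0.45 for any q: no bias. If r is above 0.45, the rate falls.

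**Cross-check from the other side.** Let a share f of non-responders and a share g of responders add treatment. Rate read = 0.45(1 − g) / [0.45(1 − g) + 0.55(1 − f)].

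- f = 30%, g = 10%: 0.405 / (0.405 + 0.385) = 51.3%. This agrees with the 20%/20% row, since about 21% leave (0.55 × 0.30 + 0.45 × 0.10) and about a fifth of them are responders.
- f = 10%, g = 20%: 0.36 / (0.36 + 0.495) = 42.1%. This is the reversed case.

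**The case against.** The best counter-argument is that the plan already leans towards a Visit 1 definition. The full analysis set is framed on intention-to-treat and needs only one dose of treatment; the per-protocol set is secondary; and Section 3.2 presents combination therapy as a choice of route. The evidence for the actual-use reading is indirect. Recording concomitant treatment defines no denominator, and secondary endpoint 1 could simply describe patients on combination therapy from the start. The visit text in 7.1.2 about opting for other treatment plans serves both cohorts and may refer only to the comparison patients. Much of this stands, and it makes the Visit 1 reading the more natural one. But the full analysis set pools capsule and other treatment, no capsule-only subset is named, and the endpoint still says using.

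It can also be said that safeguards exist. The 24-hour rule stops drug-assisted movements from counting, and secondary endpoint 2 uses the same criterion without alone, so a divergence could be seen. Both help. The first acts on single bowel movements and names medication only, while Section 4 also lists non-drug treatments such as biofeedback. The second is not the primary endpoint. Neither decides who is counted.

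A reader might infer something stronger: that the actual-use reading necessarily drops capsule failures and inflates the rate. The documents do not support this. Actual use could equally be applied by counting those who add treatment as non-responders, which would not bias the rate upwards. Nor does the plan say that those who add treatment respond less often. That is plausible, because treatment follows need, but it is an assumption.

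A reader might also take an extreme case as typical. If 20% leave and none of them respond, a true 45% reads as 56.25%, reaches 50% in 98% of trials and rejects H0 in 48%. Nothing in the documents suggests that no leaver would respond. In the less extreme cases tabulated, rejection of H0 stays at or below 5.3%.

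**Conclusion.** The concern holds in conditional form. The primary denominator is not fixed, and on a literal reading it depends on treatment used after baseline. If patients who add treatment are excluded and respond less often than the rest, the reported rate is too high; if they respond equally often there is no bias, and if more often it is too low.

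The size cannot be taken from the documents. In the illustrated range the shift from a true 45% is about 2 to 6 percentage points. That is enough to change materially the chance of an observed rate reaching 50%, but for the formal test of H0 the effect is small to modest. The ambiguity itself needs no assumption.

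This should be fixed. It is not grounds for saying that the primary result will be inflated.

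**What to change.** In 7.2.1 and 8.1, define the primary denominator as patients in the full analysis set whose Visit 1 record shows capsules prescribed and no other constipation treatment either started or continued. State that stable diet, fibre supplements and probiotics under Section 3.2 do not count as other treatment. Keep all these patients in the denominator whatever they later add, and apply the existing 24-hour medication rule to each bowel movement.

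Report two sensitivity analyses:

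1. Any treatment added in weeks 1–6 counted as non-response. This also covers added non-drug treatment, which the 24-hour rule does not name.
2. The rate in patients who used capsules alone throughout.

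The cost is a few sentences, settled before the data are seen. No new data are needed: the Visit 1 prescription, baseline treatment information and concomitant treatment at every visit are already collected. The downside is that the reported rate may be lower than under the actual-use reading.

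### The primary endpoint asks only whether the response rate reaches 50%, names no decision rule, and read literally conflicts with the stated null of 50% or less

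*Combined protocol and SAP*

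**What the plan says.** The Protocol Summary and section 7.2.1 give the same primary endpoint: "whether the response rate of patients using the Vibrabot vibrating capsules alone reaches 50" per cent. Section 7.2.1 then defines a responder: "The definition of the responder is a patient with an average weekly increase of ≥ 1 complete spontaneous bowel movement (CSBM) compared to the baseline". Neither place mentions a test, a p-value, a confidence limit or a margin.

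Section 8.1 sets H0 as a rate of at most 50%, and "H1: The effectiveness rate of vibrating capsule treatment for constipation" being above 50%. It says that if the goal is to compare effectiveness with the expected 50%, "then a one-sample proportion test can be considered for sample size calculation". The parameters of that calculation differ from the hypotheses: the null rate is 40% ("assuming a 40% success rate under the null hypothesis") and the expected rate is 50% ("here it is estimated that the effectiveness of treating constipation with vibrating capsules is 50" per cent). The result is 191 evaluable patients, 239 after 20% loss, with 300 capsule patients planned.

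Section 8.2 sets a general two-sided 0.05 level for difference tests. Section 8.3 deals with case report forms and missing data. No section says which criterion decides the primary endpoint.

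**The concern.** The endpoint sentence and the hypotheses are different criteria. A rate of exactly 50% meets the first and lies inside H0 of the second. If the sentence is applied as written to the observed proportion, it takes no account of sampling error. The report could then call the endpoint met on data that do not reject the plan's own null. Because the plan does not say which criterion governs, the choice could also be made after the data are seen. This is the only primary endpoint, and section 3.1 says the study is meant to promote consensus or guidelines for use of the capsule.

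**Working it through.** **Inputs.** Sections 7.2.1 and 8.1: reference rate 50%; null rate for sizing 40%; expected rate 50%; α = 0.05; power 80%; 191 evaluable; 20% loss; 300 planned. Section 8.2: two-sided testing. The analysed number of capsule-alone patients is not fixed, so I use n = 300 (all planned), 240 (300 × 0.80) and 191 (the stated minimum). An n of 100 is added as an assumption, because section 3.2 allows combination therapy and the endpoint covers capsule-alone patients only.

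**Step 1: reproduce the plan's figure.** n = [z√(p0(1−p0)) + 0.8416√(p1(1−p1))]² / (p1−p0)², with p0 = 0.40 and p1 = 0.50.
- z = 1.960 (two-sided): (1.960 × 0.4899 + 0.8416 × 0.5)² / 0.01 = 190.7, so 191. This matches.
- z = 1.645 (the one-sided quantile that the formula prints): 150.5, so 151. This does not match.
- 191 / 0.80 = 238.75, so 239. This matches.

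The stated size therefore rests on a 40% null and a two-sided 5% level.

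**Step 2: cut-offs.** The literal rule is met at the smallest x with x/n ≥ 0.50. The test against p0 is met at the smallest x with P(X ≥ x | n, p0) ≤ 0.025 (exact binomial).

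| n | Literal rule | Test against 50% | Test against 40% |
|---|---|---|---|
| 300 | 150 (50.0%) | 168 (56.0%) | 138 (46.0%) |
| 240 | 120 (50.0%) | 136 (56.7%) | 112 (46.7%) |
| 191 | 96 (50.3%) | 110 (57.6%) | 91 (47.6%) |
| 100 (assumed) | 50 (50.0%) | 61 (61.0%) | 51 (51.0%) |

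At n = 240, results of 120 to 135 responders meet the literal rule without rejecting H0 ≤ 50%. At 120/240 the exact 95% interval is 43.5% to 56.5%. With a one-sided 5% test the cut-offs against 50% would be 165 (55.0%) at n = 300 and 108 (56.5%) at n = 191, so the gap narrows but remains.

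**Step 3: chance that the literal rule is met.**

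| True rate | n = 300 | n = 240 | n = 191 |
|---|---|---|---|
| 50% | 52.3% | 52.6% | 50.0% |
| 45% | 4.7% | 6.8% | 8.3% |
| 40% | 0.03% | 0.11% | 0.26% |

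At a true 50% the exact test against 50% rejects 2.2%, 2.3% and 2.1% of the time. At n = 240 the literal rule also succeeds 19.3% of the time at a true 47%, and at a true 53% there is a 69.9% chance that the two criteria disagree.

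**Step 4: power under each null.** At the plan's expected rate of 50%, the test against 50% has the 2.1% to 2.3% above. The exact test against 40% has 76.5% (n = 191), 86.4% (n = 240) and 92.6% (n = 300). The 80% claim belongs to the 40% null only. For scale, with a 50% null the formula in step 1 needs 194 evaluable patients if the expected rate is 60%, and 783 if it is 55% (both rates assumed).

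**The case against.** The strongest reply is that the wording is shorthand. The documents never refer to an observed rate or a point estimate, and never say that success is declared at 50% or more. Section 8.1 supplies hypotheses at the same 50%, links a one-sample test to the aim of comparing with that figure, and section 8.2 supplies the level. Read together, these could mean that the endpoint is met when H0 is rejected. This stands in part: a reader might infer that the plan adopts a point-estimate rule, but the documents do not support that. They leave the rule undefined and open to that reading. The reply does not remove the problem, because section 8.1 offers the test only for sizing and no section ties it to the endpoint.

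A second reply is that the false-positive claim depends on the null, and this also stands. A reader might infer that the literal rule is lax whichever null applies. Against the 40% null it is stricter than the test for n = 191 to 300, with a false-positive rate below 0.3%. At an assumed n = 100 it falls just short of the test (50 against 51).

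Third, no single upper end of the disagreement zone can be given. It depends on sidedness and on the analysed number. That number is unsettled: section 8.1 imputes missing primary data in the FAS, section 8.3 says missing data are not to be filled in, and the capsule-alone subset has no stated size.

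**Conclusion.** The point holds as a conflict between the literal endpoint and the stated H0, with no rule to settle it. At two-sided 5%, exact, the zone of disagreement with H0 ≤ 50% runs from 50% to just below 56.0% (n = 300), 56.7% (n = 240) or 57.6% (n = 191), and further if few patients use the capsule alone. At the boundary of that null, the literal rule succeeds about half the time. Because section 8.1 also carries a 40% null, three cut-offs can be defended from the text, and the choice among them decides the verdict for any n = 240 result between 112 and 135 responders. The figures assume independent patients, a complete responder status for the n shown, and the two-sided level of section 8.2. This should be settled before any outcome data are analysed.

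**What to change.** In section 7.2.1 and the Protocol Summary, state that success is declared only if the lower limit of the two-sided 95% confidence interval for the capsule-alone response rate exceeds one named null value. Add that an observed rate at or above 50% is not by itself success. Name one interval method, for example exact Clopper-Pearson: at n = 300 against 50%, Wilson passes at 167 responders and the exact interval at 168. State the analysis set and denominator for capsule-alone patients. Give the null as a number, because a reference to section 8.1 would leave 40% and 50% both open. In section 8.1, use that number for H0, H1 and the sizing, and restate the power.

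The edit is short, but the cost depends on the null:
- **50%, as H0 is written.** The observed rate needed rises to about 56% to 58% (n = 300 to 191). Power at the assumed 50% rate is about 2%, so the 80% must be withdrawn or restated for a justified expected rate above 50%. If that were 60% (assumption), exact power would be 77.5% at n = 191, 86.8% at n = 240 and 92.9% at n = 300.
- **40%, as used for sizing.** The sample size stands, but H0, H1 and the endpoint wording must be changed to match, and the claim becomes that the rate exceeds 40%.

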6.2 Exclusion Criteria

1. People who are not eligible for surgery or refuse to undergo any abdominal surgery;
2. People with known or suspected gastrointestinal obstruction, stenosis, diverticulum, bleeding, malformation, and fistula.
3. People allergic to polymeric materials;

4. People implanted with cardiac pacemakers and using gastrointestinal pacemakers;
5. People with abdominal aortic aneurysms, gastrointestinal vascular lesions, ulcers, and lesions with bleeding tendencies.
6. People with dysphagia;
7. Pregnant women;
8. People with severe depression and anxiety and severe acute gastrointestinal lesions.
9. People with other conditions, so the investigator considers them not eligible for this study.

7 . Overall Design

This study is a multi-center, prospective cohort study based on real-world clinical trial design, planning to include 300 patients with chronic functional constipation to treat with Vibrabot capsules, and concurrently include ≥ 300 patients with functional constipation to treat by other methods.

During the study, it is necessary to collect the patient's basic information, baseline constipation status and treatment information, capsule intake during treatment, and concomitant medication. During the treatment phase, patients follow the doctor's advice to receive Vibrabot capsule treatment and maintain stable dietary intake and exercise according to the constipation diagnosis and treatment guidelines.

During the study, the patients need to scan the QR code or search for the electronic questionnaire "Vibrabot Health" Official Account on WeChat, and fill in the relevant information during the treatment in the electronic questionnaire in a timely and truthful manner. The treatment effect of the patients is evaluated by assessing the number of occurrences of spontaneous bowel movements (SBM) and complete spontaneous bowel movements (CSBM).

Note:

[figure not shown]
Spontaneous bowel movement: No medication used within 24 hours before bowel movement.

Spontaneous bowel movement: No medication was used within 24 hours before defecation, and there is a feeling of complete fecal evacuation.

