7.1.2 Visit Content

Each patient will undergo a series of study visits, including screening, treatment visit, and follow-up visit. The visit process is briefly described as follows:

Visit 1 (0 ~ 1 day) - Baseline/Screening Period:

This visit includes:

The patient will sign an informed consent form;

Set the inclusion/exclusion criteria;

Guide patients to fill out the questionnaire using the Official Account and complete the *Baseline Period Questionnaire* in the Official Account.

Prescription Vibrabot capsule treatment or other treatment options.

Visit 2 (Week 2 ±3 days) - Treatment Period 1:

This visit includes:

Fill out the *Daily Bowel Movement Questionnaire* in the WeChat Official Account every day, take Vibrabot capsules on time or opt for other treatment plans;

Fill out the *Constipation Symptom Self-Assessment Scale and Assessment Scale for Quality of Life with Constipation* in the Official Account every 2 treatment weeks.

Record adverse events and concomitant treatments;

Prescription Vibrabot capsules or other treatment options.

Visit 3 (Week 4±3 days) - Treatment Period 2

This visit includes:

Fill out the *Daily Bowel Movement Questionnaire* in the WeChat Official Account every day, take Vibrabot capsules on time or opt for other treatment plans;

Fill out the *Constipation Symptom Self-Assessment Scale and Assessment Scale for Quality of Life with Constipation* in the Official Account every 2 treatment weeks.

Record adverse events and concomitant treatments;

Prescription Vibrabot capsules or other treatment options.

Visit 4 (Week 6 ±3 days) - Treatment Period 3

This visit includes:

Fill out the *Daily Bowel Movement Questionnaire* in the WeChat Official Account every day, take Vibrabot capsules on time or opt for other treatment plans;

Fill out the *Constipation Symptom Self-Assessment Scale and Assessment Scale for Quality of Life with Constipation* in the Official Account every 2 treatment weeks.

Record adverse events and concomitant treatments.

Visit 5 (Week 10±3 days) - Follow-up Period:

This visit includes:

Fill out the *Daily Bowel Movement Questionnaire* in the WeChat Official Account every day;

Fill out the *Constipation Symptom Self-Assessment Scale and Assessment Scale for Quality of Life with Constipation* in the Official Account every 2 treatment weeks;

Record adverse events and concomitant treatments.

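### For patients who stop a laxative at entry, the primary responder rule can score a fall in complete bowel movements as a response, because baseline CSBM leaves out movements within 24 hours of medication

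*Combined protocol and SAP*

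**What the plan says.** - **Primary endpoint (7.2.1).** The question is "whether the response rate of patients using the Vibrabot vibrating capsules alone reaches 50" per cent. The responder rule reads: "The definition of the responder is a patient with an average weekly increase of ≥ 1 complete spontaneous bowel movement (CSBM) compared to the baseline". The rule has no term for medication in use at baseline.
- **What counts (Note in Section 7, Overall Design).** The first entry reads "Spontaneous bowel movement: No medication used within 24 hours before bowel movement". The second has the same label but plainly defines the complete movement: "No medication was used within 24 hours before defecation, and there is a feeling of complete fecal evacuation".
- **Who may enter (6.1, 6.2).** Rome IV functional constipation and consent are required. No exclusion concerns current laxative use.
- **When baseline is taken (7.1.1, 7.1.2).** The heading is "Visit 1 (0 ~ 1 day) - Baseline/Screening Period". Consent, the Baseline Period Questionnaire and the first prescription ("Prescription Vibrabot capsule treatment or other treatment options") all belong to this visit. No run-in or washout is listed.
- **Where baseline treatment is used.** Section 7 says that it is collected. Among the endpoints it appears only as a subgroup factor in item 10 of the secondary list: "gender, and baseline treatment status) responding to vibrating capsule treatment and at the end of follow-up". Section 8 gives no rule for baseline medication in the primary analysis.

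**The concern.** The change score compares two periods in which the 24-hour exclusion may remove very different numbers of movements. For a patient on a daily laxative it removes every baseline movement. Once that patient is on capsules alone, it removes none. Part or all of the required gain of 1 CSBM a week can then come from stopping the laxative, whatever the capsule does.

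The primary result is a single-arm proportion set against a fixed threshold, so no control group cancels this. Section 3.1 says that the results are meant to support a consensus or guidelines for use. A headline rate that mixes added bowel movements with a change in what is counted would be hard to interpret for that purpose.

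**Working it through.** **The plan's own figure.** Section 8.1 gives 191, and 239 after 20% loss. With p0 = 0.40, pT = 0.50, power 0.80 and two-sided alpha 0.05:

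n = [1.960 × √(0.40 × 0.60) + 0.842 × √(0.50 × 0.50)]² / 0.10² = 190.7, so 191; and 191 / 0.80 = 238.75, so 239.

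Both reproduce, and this point does not change them. The calculation uses a null of 40%, while the stated H0 and 7.2.1 use 50%. That is a separate matter; the 50% threshold is used below.

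**A worked patient (assumed figures).** On a daily laxative the patient has 3 complete movements a week, each within 24 hours of a dose. Baseline CSBM is 0. On capsules alone the patient has 1.5 complete movements a week, all unaided, so CSBM is 1.5. The change is +1.5 and the patient is a responder, while total complete movements fell from 3 to 1.5.

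**How easily a zero baseline yields a response.** Assume Poisson counts averaged over 6 weeks. The rule then needs at least 6 CSBMs in total, with probability P(Poisson(6λ) ≥ 6) at a weekly rate λ:

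| λ on capsules alone | Probability of being a responder |
|---|---|
| 1.0 | 55% |
| 1.25 | 76% |
| 1.5 | 88% |

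These do not depend on how many complete movements the laxative gave.

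**Effect on the primary rate.** Let f be the share of the capsule-alone group who stop a laxative at entry. Assume a true rate of 45%, and 75% scored as responders among those who switch (close to the λ = 1.25 row). The expected rate is (1 − f) × 0.45 + f × 0.75.

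Take n = 300 × 0.80 = 240 evaluable. The result exceeds 50% at two-sided 0.05 when the count is above 120 + 1.96 × √60 = 135.2, so at least 136 responders. Exact binomial probabilities:

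| f | Expected rate | Chance of beating 50% |
|---|---|---|
| 0 | 45% | 0.02% |
| 20% | 51% | 4.5% |
| 30% | 54% | 22% |
| 40% | 57% | 57% |

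If the true rate is exactly 50%, the chance is 2.3% with no switchers. With 20% switched the expected rate is 0.8 × 0.50 + 0.2 × 0.75 = 55%, and the chance is 33%.

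The documents give neither f nor the 75%. Both tables are illustrations.

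**The case against.** 1. **The baseline instrument is not visible.** The items and recall period of the Baseline Period Questionnaire are not in the documents, and it may ask about medication-free days. This stands as a limit. No section says that it does, and 7.2.1 and Section 8 do not refer to such a measure.
2. **A baseline of 0 is the extreme case.** A reader might infer that every laxative user starts at 0. That holds only when every movement follows medication within 24 hours, as with daily use. Intermittent users keep the CSBMs from their medication-free days.
3. **The bias need not always be upward.** A reader might infer that it is. If a laxative acts beyond 24 hours, late movements count as spontaneous, raise baseline CSBM and make a gain harder after stopping. The documents do not settle the direction for intermittent users.
4. **The size may be small.** With 20% switched the chance of a false success is only 4.5%; the 57% needs 40% switched and 75% of them responding. Using 240 also assumes that all 300 capsule patients use capsules alone, although Section 3.2 allows combination therapy. With 150 evaluable (an assumption) the chance at a 57% rate is 37%. This stands.
5. **CSBM is meant to measure unaided function.** Going from none to 1.5 unaided complete movements a week is a gain of a kind, and whether it counts as benefit is a choice of estimand. That is a reason to keep the definition. It is also a reason to show total complete movements beside it, since coming off a laxative and having more movements are different claims.
6. **The study is partly protected.** Item 10 reports response by baseline treatment status. Items 7 and 8 use PAC-QOL and PAC-SYM scores, which do not depend on the 24-hour rule. Items 3 and 6 use an absolute threshold of 3 SBMs a week, so a zero baseline cannot by itself create success there. This is true, but none of these is the primary rate. Item 10 uses the same CSBM change and could make prior laxative users look like better responders.

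**Conclusion.** The point holds as a gap in the definition of the primary endpoint. As written, the rule can count as a responder a patient who stops a laxative and then has fewer complete movements. For daily users who switch to capsules alone, the effect on the rate is upward.

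The size is unknown. Under the stated assumptions, the chance of wrongly beating 50% runs from 4.5% at 20% switched to 57% at 40%. It rests on the share who switch, their responder rate, the number using capsules alone, and what the baseline questionnaire asks.

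A reader might go further and infer that a result above 50% would be spurious, or that the study ignores baseline treatment altogether. The documents support neither: they do not give the share who switch, and baseline treatment is collected and used in item 10. This should be fixed; it does not invalidate the design.

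**What to change.** Keep the responder definition in 7.2.1 and add the following.

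1. **Baseline Period Questionnaire:** record the number of laxative days in the look-back, and complete movements both with and without the 24-hour rule.
2. **Daily Bowel Movement Questionnaire:** record the same total of complete movements, with or without medication.
3. **Section 8:** pre-specify that the capsule-alone primary rate is reported separately for patients with and without baseline constipation medication.
4. **Section 8:** add a sensitivity analysis in which a baseline medication user whose total complete movements fall is not counted as a responder.
5. **Claim:** state that the rate reaches 50% only if the result also holds in patients without baseline medication or in that sensitivity analysis. This is a condition added to the primary test, so it cannot raise the false-positive rate.

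A stricter option would require baseline medication users to gain at least 1 a week on both counts. It over-corrects. A patient who matches a laxative total of 3 a week with 3 unaided movements would need 6 × (3 + 1) = 24 in 6 weeks, and P(Poisson(18) ≥ 24) is only 10%.

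Whether to have a washout is a clinical decision for the sponsor and investigators, and none is proposed here.

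The cost is one or two items in an existing electronic questionnaire and a few sentences in Section 8. No visit is added and no patient is dropped from the primary analysis. The supporting rate may be less favourable, and less precise in the smaller group.
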